8.1.7 Safety Analysis

Safety analysis will be based on the incidence, intensity, and type of adverse events, and clinically significant changes in the patient's physical examination, vital signs, and clinical laboratory results. Safety variables will be tabulated and presented for all patients in the study. Exposure to study drug and reasons for discontinuation of study treatment will be tabulated. Group comparisons will be performed using chi-square or Fisher's exact test.

All adverse events occurring on study will be listed in by-patient data listings. Treatment emergent events will be tabulated, where treatment emergent is defined as any adverse event that occurs after administration of the first dose of study drug and through the End of Study visit or up through 30 days after the last dose of study drug, any event that is considered drug-related regardless of the start date of the event, or any event that is present at baseline but worsens in intensity or is subsequently considered drug-related by the Treating investigator and/or Lead Principal Investigator. Events that are considered related to treatment (possibly, probably or definitely drug-related) will also be tabulated. Deaths, serious adverse events and events resulting in study discontinuation will be tabulated.

Change from baseline in clinical laboratory parameters will be summarized across time on study, and the frequency of clinically significant abnormal laboratory values will be tabulated. Similarly, changes in vital sign parameters will be summarized over time, and any abnormal values will be tabulated.

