19) All patients are required to have a sample for MRD collected at screening, at the End of Treatment visit, and at any other time a Bone Marrow biopsy/aspirate is collected as SOC. Additionally, FFPE or BMA slides from diagnosis will be required for calibration of MRD by NGS for all patients. If CR is recorded between screening and EOT, a Bone Marrow Biopsy can be indicated. However, if CR is suspected within 3 months of EOT, it is acceptable to wait for the EOT BM biopsy. It is expected that samples will be collected at a minimum of two time-points for each patient. Refer to lab manual for collection and shipping instructions. Central analysis includes MRD by multi-parameter flow cytometry and MRD by gene sequencing.							
20) AEs will be collected from the time of signing informed consent to 30 days following the last dose of treatment. Please refer to section 9 for specific collection requirements.							
21) Assessment for disease progression in subjects who did not progress during treatment. At least every 3 months (+/- 30 days) for 2 years from safety follow-up visit (which must be 28days (+/- 3 days) post-last study treatment).							
22) lenalidomide must be prescribed through and in compliance with the lenalidomide REMSTM program of Celgene Corporation. Prescriptions must be filled within 7 days. Consideration should be given to prescribing lenalidomide 5 to 7 days in advance of Day 1 of each cycle to allow time for required patient and prescriber surveys, and drug shipment to patient. Any unused lenalidomide will be counted and documented by each site.							
23) Control Arm: Lenalidomide should continue at best tolerated dose of either 10 mg or 15 mg on days 1-28. If the 10 mg dose is tolerated for three cycles, it can be escalated to 15 mg per dose.							

Assessment	Screening ²	Cycles 1-12				EOT	Long-term follow-up
		1	8	15	22		
Day	-42 to -1						
24) Experimental Arm: lenalidomide dosing Days 1-21. Cycle 1-4 lenalidomide will be administered at 25 mg daily. Cycles 5-12 lenalidomide will continue at best tolerated dose days 1-21. lenalidomide should be taken in the evening at approximately the same time each day.							
25) Cycles 1-4: Ixazomib at 3-4 mg Days 1, 8, 15. Cycles 5+ Ixazomib at best tolerated dose on Days 1, 8, 15. Ixazomib should be taken on an empty stomach or at least 1 hour before or 2 hours after a meal.							

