Bone Marrow Biopsy	Quantify percent myeloma cell involvement, and obtain bone marrow aspirate for conventional cytogenetics and fluorescent in situ hybridization. Required specimen for calibration step for MRD evaluation by gene sequencing. For subjects who sign consent for correlative samples, an additional aspirate sample should be collected at screening (Section 8). Bone marrow biopsy/aspirate performed outside of the 42 day window may be considered for inclusion. Please contact the Lead Principal Investigator and/or the CRA on a case-by-case basis.
Plasmacytoma Evaluation	May be performed by physical exam or imaging, whichever is clinically indicated and at the treating investigator's discretion.

Skeletal Survey	May be within 42 days of planned treatment start (does not need to be repeated if within 42 days). Includes: lateral radiograph of the skull, anteroposterior and lateral views of the spine, and anteroposterior views of the pelvis, ribs, femora, and humeri.
Neurotoxicity Assessment	Includes Neurotoxicity Questionnaire (Appendix 13.4)
QOL Assessment	Patient reported survey (Appendix 14.5)
Adverse Events	Only SAEs considered related to study procedure need to be reported.
Correlative Samples	Peripheral blood and bone marrow aspirate samples collected at screening. Buccal mucosa swab will be collected at screening only

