10.2 Causality

Using the following criteria, the relationship of the AE to the study drug should be assessed as follows: Definite, Probably, Possible, Unlikely, Unrelated.

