10.3 Adverse Event Reporting Procedures

Information about all AEs, whether volunteered by the subject, discovered by investigator questioning, or detected through physical examination, laboratory tests or other means, will be collected and recorded and followed as appropriate.

All AEs (e.g., any new event or worsening in severity or frequency of a pre-existing condition or laboratory finding) with an onset date on or after the first dose of treatment through 30-days after the last treatment dose must be promptly documented on the appropriate CRF in eVelos. Any SAE (Section 10.4) which is considered related to study procedures and occurs after informed consent but before Cycle 1 Day 1 must be reported. Details of the event must include severity, relationship to study drug, duration, action taken, and outcome. All AEs must be followed to resolution or stabilization regardless of relationship to study drug.

All AEs that are considered related to study drug must be followed to resolution or stabilization if improvement is not expected.

AEs must be reported from the date of the first dose of treatment through 30 days post-last dose of study treatment or initiation of a new anti-cancer therapy, whichever occurs first. If a subject is enrolled but discontinues study prior to receiving any study drug, only SAEs that are considered related to study procedures must be reported through the end-of-study visit. AEs which completely resolve and then recur should be recorded as a new AE. For subjects who complete the end of study visit less than 30 days following their last dose of study drug, a follow up of ongoing AEs should be attempted by telephone, and documented in the subject's source.

AEs continuing at 30 days post-last dose should have a comment in the source by the Treating Investigator that the event has stabilized or is not expected to improve. SAEs continuing at 30 days post-last dose should be followed until resolution or stabilization.

Whenever possible, the Common Terminology Criteria for Adverse Events (CTCAE) version 4.0 should be used to describe the event and for assessing the severity of AEs. Any events representing a change in the CTCAE Grade need to be reported on the AE case report form. This includes any change in laboratory values.

For AEs not adequately addressed in the CTCAE, the severity table below may be used:

Severity	Description

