GRADE 1 – Mild	Transient or mild discomfort; no limitation in activity; no medical intervention/therapy required.
GRADE 2 – Moderate	Mild to moderate limitation in activity—some assistance may be needed; no or minimal medical intervention/therapy required.
GRADE 3 – Severe	Marked limitation in activity, some assistance usually required; medical intervention/therapy required, hospitalizations possible.
GRADE 4 – Life-threatening	Extreme limitation in activity, significant assistance required; life-threatening (immediate risk of death); significant medical intervention/therapy required, hospitalization or hospice care probable.
GRADE 5 – Fatal	Death

Any condition, laboratory abnormality, or physical finding with an onset date prior to the subject signing consent for study participation is considered to be pre-existing in nature and part of the subject's medical history.

The Treating Investigator is responsible for evaluating all AEs for relationship to study drug and for seriousness, obtaining supporting documents, and determining that documentation of the event is adequate. The Site or Lead Principal Investigator may delegate these duties to Sub-investigators and must ensure that these Sub-investigators are qualified to perform these duties under the supervision of the Principal Investigator and that they are listed on the FDA Form 1572 and delegation log.

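### The treatment-emergent definition in 8.1.7 sets no lower time limit for drug-related events and admits baseline events that have not worsened, so some events that began before the first study dose can be counted

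*Combined protocol and SAP*

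**What the plan says.** Section 8.1.7 builds its treatment-emergent definition from three limbs.

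- **Limb 1** is conventional: events after the first dose of study drug, through the end-of-study visit or 30 days after the last dose.
- **Limb 2** adds "any event that is considered drug-related regardless of the start date of the event".
- **Limb 3** adds an event that "is present at baseline but worsens in intensity or is subsequently considered drug-related by the Treating investigator" or by the lead investigator. The two conditions are joined by *or*, so worsening is not required.

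Treatment-emergent events are then tabulated, and 8.1.7 compares groups by chi-square or Fisher's exact test. Safety and tolerability of IRd versus R is a secondary objective (2.2) and endpoint (3.2).

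The start of adverse-event recording is described in more than one way.

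- Schedule of Events, the note printed as number 20: "AEs will be collected from the time of signing informed consent to 30 days following the last dose of treatment".
- Section 4.2.1, screening: "Only SAEs considered related to study procedure need to be reported".
- Section 10.3: AEs "with an onset date on or after the first dose of treatment through 30-days after the last treatment dose must be promptly documented", and again "AEs must be reported from the date of the first dose of treatment through 30 days post-last dose of study treatment".
- Section 10.3 also says that a condition with an "onset date prior to the subject signing consent for study participation is considered to be pre-existing in nature" and belongs to the medical history.

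Section 10.2 fixes the reference for causality: "the relationship of the AE to the study drug should be assessed as follows".

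**The concern.** A treatment-emergent table is meant to show what appeared or worsened after study treatment began. Limbs 2 and 3 can admit events that did neither.

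This trial is more exposed than most because lenalidomide is the whole of the control arm, part of the experimental arm, and a drug that many patients already take. Section 5.1 allows enrolment during the first 0 to 6 months of lenalidomide maintenance. Section 1.9 describes all enrolled subjects as already on it, although 5.1 says that this is not required at consent. Section 10.2 refers to study drug, but the molecule is the same before and after Cycle 1 Day 1, so an investigator could reasonably call an earlier lenalidomide toxicity drug-related.

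At stake is the IRd versus R comparison of adverse-event incidence. Events common to both arms would raise both rates and narrow the difference. The trial is also open-label, and under limbs 2 and 3 the relatedness judgement itself decides whether an early event counts.

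**Working it through.** The plan states no adverse-event rate, safety power or count of pre-study events, so there is no figure of its own to reproduce. The main check is textual; the arithmetic that follows is conditional.

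**Step 1. Which early events can reach the table?**

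| Onset | Recording rule | Can it be counted as treatment-emergent? |
|---|---|---|
| Before consent | 10.3: medical history | Not through limb 2 if 10.3 is followed. Limb 3 speaks of baseline events, so one later judged related could be brought in without worsening |
| Consent to first dose | Schedule note: collected. 4.2.1: procedure-related SAEs only. 10.3: AE recording starts at first dose | Yes through limb 2 if the schedule note is followed; essentially no if 4.2.1 and 10.3 are followed |
| On or after first dose | All agree | Yes, properly, through limb 1 |

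Two routes remain:

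- **(a) The consent-to-first-dose window.** Screening is nominally up to 42 days (4.2.1). A one-week break from off-protocol lenalidomide is suggested, not required (5.1).
- **(b) Relabelling of unworsened baseline events.** Baseline material exists to relabel: 4.2.1 records current symptoms and residual toxicities, and the Schedule of Events asks for the baseline neuropathy grade.

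**Step 2. What would equal carry-over do?** Let p be an arm's true on-study incidence, and let b be the share of patients with a carried-over event, equal in both arms and independent of on-study events. The counted rate is

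p′ = p + b(1 − p),

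so the difference becomes (1 − b)(p_E − p_C).

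Inputs: 30 per arm (8.1.1). Assumed, because the documents give none: p_C = 20%, p_E = 50%, two-sided 5% test.

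Example at b = 10%: control 0.20 + 0.10 × 0.80 = 0.28; experimental 0.50 + 0.10 × 0.50 = 0.55; difference 27 points.

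| b | Control | Experimental | Difference | Power, normal approx. | Power, Fisher |
|---|---|---|---|---|---|
| 0 | 20% | 50% | 30.0 | 69% | 60% |
| 5% | 24% | 52.5% | 28.5 | 63% | 53% |
| 10% | 28% | 55% | 27.0 | 57% | 47% |
| 20% | 36% | 60% | 24.0 | 46% | 37% |
| 30% | 44% | 65% | 21.0 | 37% | 28% |

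If 4.2.1 and 10.3 are followed and no unworsened baseline event is relabelled, b is about 0 and the first row applies.

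**Step 3. What if carry-over differs by arm?** Same assumed rates, 10% carry-over in one arm only:

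- control only: 0.50 − 0.28 = 22 points, so the difference is understated;
- experimental only: 0.55 − 0.20 = 35 points, so it is overstated.

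The direction is therefore not determined. For scale, one extra patient counted in one arm moves that arm's rate by 1/30 = 3.3 points.

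**The case against.** The strongest reply is that the recording rules already do the work.

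- Under 10.3, onset before consent is medical history. That covers nearly all of the up to six months of prior lenalidomide.
- Sections 4.2.1 and 10.3 agree in excluding routine AEs before first dose, and 10.4.3 starts SAE collection at the start of treatment. The adverse-event row of the schedule, as it reads in the available text, is blank at screening.
- The schedule note goes on to defer to section 9 for collection requirements. Section 9 is now Correlative Samples, so this looks like an outdated pointer to the adverse-event section.
- Section 10.1 treats a previous condition as an AE only if it has increased in severity or frequency since study drug was given.
- Limb 2 follows directly on the 30-day limit, so it may be meant to keep late related events. Section 10.4.3.1 requires related SAEs to be reported after ixazomib treatment has ended.
- The table is secondary. By-patient listings and separate tabulations of related events, deaths, SAEs and discontinuations will also be produced.

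Most of this stands, and it confines the problem to routes (a) and (b). It does not remove it. Limb 2 does not say that it concerns late events only. Limb 3 does not require worsening, which is at odds with 10.1. The schedule note still says consent.

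A reader might infer that lenalidomide toxicity from before the study enters both arms and dilutes the safety comparison. The documents do not support that. Onset before consent is classed as history, no carry-over rate is given, and dilution needs roughly equal carry-over in the two arms, which open-label relatedness judgements do not guarantee. That handling would vary from site to site is likewise an inference from the conflicting text, not something the plan states.

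**Conclusion.** The definition is faulty as written: limb 2 has no lower time limit, limb 3 admits baseline events that have not worsened, and the schedule note disagrees with 4.2.1 and 10.3 on when recording begins. Events that began before the first study dose can therefore be counted, but only through the two routes identified.

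The effect on IRd versus R is probably small, and its sign is not known. The shrinkage by (1 − b) rests on assumed incidence rates, equal carry-over, and independence from on-study events; with unequal carry-over the bias can run either way. Severity is minor: a secondary safety tabulation is affected, and the MRD endpoint is not.

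**What to change.** In 8.1.7, define a treatment-emergent event as one with onset, or worsening in grade from baseline, on or after the first dose of study treatment and through 30 days after the last dose, plus any later-onset event judged related to study treatment. This keeps a late-event purpose for limb 2 if one was intended. Remove the start-date exemption for events that begin before the first dose, and remove the part of limb 3 that needs no worsening.

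Reconcile the schedule note with 4.2.1 and 10.3 so that one start date governs recording, and correct its pointer to section 9. If events between consent and first dose are wanted, list them separately as pre-treatment events.

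The cost is wording in 8.1.7 and one schedule note. No new data are needed.

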9. CORRELATIVE SAMPLES

In addition to the required bone marrow aspirate sample for MRD analysis collected at screening and time of response, for patients who consent, we will collect samples including bone marrow core biopsy and aspirate, peripheral blood, and buccal swabs. Peripheral blood and bone marrow samples will also be collected at the time of achievement of at least CR, or better, at 1 year after randomization (providing that the patient is at least in CR and no recent bone marrow evaluation within 1-2 months). Correlative samples should be collected at any time that bone marrow is performed as SOC outside of these time points. Additional evaluations may include proteomics, gene expression profiling, microRNA, SNP analysis, analysis of genetic variants

Table 8-1 Correlative Sample Schema

Visit	Bone Marrow Aspirate	Peripheral Blood	Plasma	Serum	Buccal Mouth Swab
Screening	X	X	X	X	X
At any time after randomization after achievement of CR or better*	X	X	X	X	
End of Treatment	X	X	X	X	

Refer to the laboratory manual for collection procedures, processing, and shipments

10. ADVERSE EVENTS

10.1 Adverse Event Definition

Adverse event (AE) means any untoward medical occurrence in a patient or subject administered a pharmaceutical product; the untoward medical occurrence does not necessarily have a causal relationship with this treatment. An AE can therefore be any unfavorable and unintended sign (including an abnormal laboratory finding), symptom, or disease temporally associated with the use of a medicinal (investigational) product whether or not it is related to the medicinal product. This includes any newly occurring event, or a previous condition that has increased in severity or frequency since the administration of study drug.

An abnormal laboratory value will not be assessed as an AE unless that value leads to discontinuation or delay in treatment, dose modification, therapeutic intervention, or is considered by the investigator to be a clinically significant change from baseline.

An unexpected AE is any adverse drug event, the specificity or severity of which is not consistent with the current IB or prescribing information for a marketed compound. Also, reports which add significant information on specificity or severity of a known, already documented AE constitute unexpected AEs. For example, an event more specific or more severe than described in the IB would be considered “unexpected”.

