Serum Chemistry ¹⁰	X	X	[X]	[X]		X	
Pregnancy Test ^{11, 12}	X	X				X	
Disease Assessment							X ²⁰
β2-microglobulin	X						
SPEP, UPEP ¹³	X	X		[X]		X	
BM Aspirate/biopsy, cytogenetics, FISH ¹⁴	X					X	
Quantitative Immunoglobulins	X	X		[X]		X	
SFLC	X	X		[X] ¹⁵		X	

Assessment	Screening ²	Cycles 1-12				EOT	Long-term follow-up
		1	8	15	22		
Day	-42 to -1						
Neurological Assessment ¹⁶	X	X				X	
QOL Assessment ¹⁶	X	X				X	
Correlative Samples ¹⁷	X	X				X	
Sample for MRD Analysis ^{18,∞}	X					X	
Adverse Events ¹⁹		X					
Control Arm							
Lenalidomide ^{21,22, 28}		Continuous Days 1-28			X ²⁶	X ²⁶	
Experimental Arm							
Lenalidomide ^{21,23, 28}		Continuous Days 1-21			X ²⁶	X ²⁶	
Ixazomib ²⁴		X	X	X			
Dexamethasone ²⁵		X	X	X	X		
Survival and Evaluation of Second Primary malignancies							X ²⁷

- + Documented informed consent must be obtained prior to any screening procedures but can be obtained prior to the screening window of 42 days
- ♥ Informed consent is valid for 42 days – if the patient has not been enrolled/randomized within the screening window, re-consent must be obtained prior to submitting the registration packet for review
- * Variations of ± 3 days of the scheduled visit are permitted
- ∞ Using diagnostic bone marrow samples for the Adaptive ID (calibration) testing is preferred as these will have the highest disease burden. If the calibration is successful, please submit the screening bone marrow samples to determine MRD status prior to study entry. If DNA identification from the diagnostic sample fails, procure additional slides from the screening marrow as these can be used for both calibration and MRD tracking. Contact the UC Multi-Site Coordinator prior to submitting additional samples, if the initial ID test fails.

[X] Only as clinically indicated

2) Includes neuropathy history and documentation of the CTCAE grade if peripheral neuropathy is present at baseline.

Assessment	Screening ²	Cycles 1-12				EOT	Long-term follow-up
		1	8	15	22		
Day	-42 to -1						

- 3) May be within 42 days of planned treatment start. Includes: lateral radiograph of the skull, anteroposterior and lateral views of the spine, and anteroposterior views of the pelvis, ribs, femora, and humeri. Skeletal surveys performed outside of the 42-day window may be considered for inclusion 6 or 8 weeks prior to randomization. Please contact the Lead Principal Investigator and/or/CRA on a case-by-case basis.

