- All other non-hematologic toxicity (except for alopecia) must have resolved to \leq Grade 1 or to the patient's baseline condition

If the patient fails to meet the above-cited criteria for initiation of the next cycle of treatment, dosing should be delayed for 1 week. At the end of that time, the patient should be re-evaluated to determine whether the criteria have been met. If the patient continues to fail to meet the above-cited criteria, delay therapy and continue to reevaluate. The maximum delay before treatment should be discontinued will be 3 weeks or at the discretion of the Principal Investigator. Any delay greater than 21 days must be reviewed with the Lead Principal Investigator if the treating investigator believes that continued treatment is in the subject's best interest and confirmation of clinical benefit (absence of disease progression).

The following tables outline dosing recommendations for Ixazomib, lenalidomide and Dexamethasone.

Dosage adjustments for hematologic toxicity are outlined in Table 6-5

Table 7-5 Ixazomib and Lenalidomide Dose Adjustments for Hematologic Toxicities^{a, b}

Criteria	Action
If platelet count decreased to Grade 3 with clinically significant bleeding or Grade 4 $< 25 \times 10^9/L$ on any dosing day (other than Day 1)	
 • Ixazomib dose and lenalidomide should be withheld. • Complete blood count (CBC) with differential should be repeated at least twice weekly until the platelet counts have exceeded the pre-specified values (see Section 6.3.1) on at least 2 occasions. • Once resolved to Grade ≤ 1: 
 ○ 1st occurrence – decrease lenalidomide by 1 dose level; ixazomib may be reinitiated without dose reduction on the first occurrence. ○ 2nd occurrence - decrease ixazomib 1 dose level and resume len at its most recent dose ○ 3rd occurrence – decrease len 1 dose level from previous dose ○ 4th occurrence – decrease ixazomib 1 dose level from previous dose
Within-Cycle Dose Modifications	
Day 1 of Cycle Dose Modifications	
 • 1st occurrence – decrease lenalidomide 1 dose level • 2nd occurrence – decrease ixazomib 1 dose level • 3rd occurrence – decrease lenalidomide by 1 additional dose level • 4th occurrence – decrease ixazomib by 1 additional dose level
Neutrophil count (ANC) decreased Grade 3 (ANC 500-1000/mm ³) or > Grade 3 with fever (temperature $>38.5^{\circ}\text{C}$)	

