AEs may be spontaneously reported by the patient and/or in response to an open question from study personnel or revealed by observation, physical examination, or other diagnostic procedures. Any clinically relevant deterioration in laboratory assessments or other clinical finding is considered an AE. When possible, signs and symptoms indicating a common underlying pathology should be noted as one comprehensive event. For SAEs, the investigator must determine both the intensity of the event and the relationship of the event to study drug administration. For serious pretreatment events, the investigator must determine both the intensity of the event and the relationship of the event to study procedures. If a subject is permanently withdrawn from the study because of a SAE, this information must be included in the initial or follow-up SAE report as well as the appropriate form for Study Discontinuation.

The Treating Investigator is responsible for notifying their respective Institutional Review Board (IRB) or Independent Ethics Committee (IEC) in accordance with local regulations of all SAEs. Events occurring at a participating site may be reported to the University of Chicago IRB if they meet current reporting criteria.

The University of Chicago will be responsible for notifying the Regulatory Agencies where required as described in section 10.4.3.2.

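### Sections 10.1, 10.3 and 10.4.3 give conflicting rules for when a laboratory abnormality is an adverse event, so AE-based cytopenia rates depend on which rule is followed

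*Combined protocol and SAP*

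**What the plan says.** Section 10.1 sets a restrictive rule: "An abnormal laboratory value will not be assessed as an AE unless that value leads to discontinuation or delay in treatment, dose modification", or to a therapeutic intervention, or unless it "is considered by the investigator to be a clinically significant change from baseline".

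Section 10.3 sets an inclusive rule: "Any events representing a change in the CTCAE Grade need to be reported on the AE case report form", followed by "This includes any change in laboratory values". No condition of action or significance is attached.

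Section 10.4.3 has a third wording: "Any clinically relevant deterioration in laboratory assessments or other clinical finding is considered an AE".

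Section 8.1.7 tabulates treatment-emergent events and states "Group comparisons will be performed using chi-square or Fisher's exact test". It also summarizes change from baseline in laboratory parameters over time and tabulates abnormal values classed as clinically significant, without defining that term. It plans no comparison of grades derived from the laboratory values.

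The Schedule of Events requires hematology and chemistry on Day 1 of each cycle and at end of treatment, in both arms. Days 8 and 15 are marked "Only as clinically indicated", and Section 4.2.2 agrees. Table 7-5 keys its within-cycle platelet rule to a low count "on any dosing day (other than Day 1").

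**The concern.** Safety and tolerability of IRd against lenalidomide alone is a secondary objective (Section 2.2) and endpoint (Section 3.2), and AE frequencies are to be tested between arms. Cytopenias matter in that comparison: Table 1-3 gives any-grade thrombocytopenia 28%, anemia 26% and neutropenia 25% for oral ixazomib combinations.

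If the same count is an AE under one section and not under another, part of any reported cytopenia rate reflects recording. Section 4.4 plans 8 centers, each of which would have to choose a rule. Under 10.1 the status of a value turns partly on what was done to treatment and partly on a judgement made by someone who knows the arm. The laboratory frequency table in 8.1.7 does not repair this, because it rests on the same undefined judgement.

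**Working it through.** The plan gives no figure to reproduce, so the check is mainly a comparison of texts.

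**Step 1. Where the rules agree and part.**

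| Laboratory finding | 10.1 | 10.3 | 10.4.3 |
|---|---|---|---|
| Day 1 ANC below 1,000/mm³, so the next cycle is delayed (7.3.1) | AE, through the delay | Report if the grade changed | AE if clinically relevant |
| Neutrophils move from Grade 1 to Grade 2, no action, judged significant | AE | Report | AE if clinically relevant |
| Neutrophils move from Grade 1 to Grade 2, no action, not judged significant | Not an AE | Report | Depends on the meaning of clinically relevant |

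The third row is the conflict: 10.1 and 10.3 cannot both be followed there.

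**Step 2. Could the conflict differ by arm?** The criteria for starting a cycle (ANC at least 1,000/mm³, platelets at least 75,000/mm³) are not arm-specific, so a Day 1 delay makes an AE in either arm. The within-cycle hematologic rules in Table 7-5 are written for ixazomib with lenalidomide and call for counts at least twice weekly after a hold. The control arm has dose levels (Table 7-4) but no hematologic action table of its own. IRd also has more drugs that can be modified. Arm dependence is therefore a supported inference, not something the text states.

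**Step 3. What a site difference alone does.** Recorded rate = true rate × share recorded. Assume, for illustration only, a true rate of 28% in both arms, half the patients in each arm at sites recording everything, and half at sites recording 50%. Each arm then shows 0.28 × (0.5 × 1 + 0.5 × 0.5) = 0.21. Both rates fall and no gap appears. Randomization is not stratified by center, so balance within a center holds only on average.

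**Step 4. What an arm difference would do, if there were one.** Inputs: 30 per arm (8.1.1), a true rate of 28% in both arms, and the two-sided 5% level that 8.1 gives for secondary analyses. The recording shares are assumptions. The chance of rejection comes from exact enumeration over two binomials.

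| Shares recorded | Recorded rates | Fisher | Chi-square |
|---|---|---|---|
| 100% and 100% | 28% and 28% | 2.6% | 4.9% |
| 90% and 70% | 25.2% and 19.6% | 4.3% | 7.9% |
| 90% and 50% | 25.2% and 14.0% | 11.4% | 18.9% |
| 90% and 30% | 25.2% and 8.4% | 27.8% | 42.4% |

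This shows sensitivity to differential recording between whole arms. It does not estimate what will happen here: the documents give no recording shares, and the 28% comes from ixazomib combinations, not lenalidomide alone.

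**Step 5. Would the mandatory counts be a clean basis for comparison?** In IRd, lenalidomide stops after Day 21, so Day 1 follows 28 − 21 = 7 days without it. The last ixazomib dose is on Day 15, giving 28 − 15 = 13 days without it. In control, lenalidomide runs through Day 28, giving 28 − 28 = 0 days. A scheduled Day 1 count thus follows a recovery interval in one arm only and may understate cytopenia on IRd.

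**The case against.** **10.3 may cover only findings already classed as AEs.** On that reading it asks for grade changes within an established event, and the conflict disappears. The text does not say so, and its sentence on laboratory values points the other way.

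**The band of disagreement is limited.** Values that delay or change treatment, or that are judged significant, are AEs under 10.1 as well. This stands: the conflict concerns unactioned grade changes, mostly the less severe ones.

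**The laboratory analysis already covers this in part.** The change-from-baseline summary does not depend on AE status. This also stands, but the summary does not compare grades between arms.

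**Stronger readings the documents do not support.** A reader might infer that the same count is more often an AE on IRd because that arm has more dosing days. It has more drugs but fewer dosing days: lenalidomide on 21 days, with ixazomib on Days 1, 8 and 15 falling inside them and dexamethasone adding Day 22 in Cycles 1-4, against 28 days in control. A reader might also put a number on a false gap between arms. That needs a whole arm to be recorded under a different rule, and nothing in the text says so. A site that follows 10.1 does so for both arms.

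**Table 7-5 does not order a count.** It can be read as saying only what follows when a low count is found, and the schedule permits counts on those days. That is fair, so this is a separate question of consistency and not evidence of bias.

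**Conclusion.** The conflict between 10.1, 10.3 and 10.4.3 is in the current text and affects the AE-based safety comparison in 8.1.7. AE-based cytopenia rates will vary with the rule a site adopts. A difference by arm is possible, since the trial is open-label and the action rules differ by regimen. Its size and direction are unknown, and the enumeration in the working is conditional on assumed shares. The primary endpoint and the change-from-baseline summary are untouched. This should be settled before the safety analysis is run. As the plan stands, a between-arm difference in AE-coded cytopenias could not be cleanly separated from a difference in recording.

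**What to change.** 1. State one laboratory-AE recording rule and use it in Sections 10.1, 10.3 and 10.4.3.
2. In Section 8.1.7, compare hematologic and chemistry toxicity by each patient's worst CTCAE grade (version 4.0, as 10.3 names), derived from all recorded laboratory values regardless of AE status. Report the number of counts per patient by arm beside it.
3. Show the same comparison restricted to Day 1 and end-of-treatment counts as a sensitivity analysis only. State that Day 1 follows a week without lenalidomide or ixazomib in IRd but not in control, and so may understate IRd cytopenia.
4. Separately, reconcile the optional mark on Days 8 and 15 in the Schedule of Events with the Table 7-5 rule for counts on dosing days other than Day 1. Which way to resolve it is a clinical decision and is not proposed here.

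The cost is protocol wording, one derived table and its sensitivity version. No new visits or samples are needed for the analysis change, provided unscheduled values are in the database; any that are not would have to be entered from source. The drawback is that unscheduled counts may be more frequent in one arm, which raises the chance of catching a low value there. The summary of counts per patient makes that visible but does not remove it.
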